4.7. Outcomes

The primary outcome is death within 30 days after positive test for SARS-CoV-2, obtained from the Danish Register of Causes of Deaths.²⁷

Secondary outcomes include hospital admission (in- or acute outpatient stay lasting > 12 hours) at day of or within 30 days after a positive test in patients not already admitted before the date of the test. In addition, outcomes include ICU admission, mechanical ventilation, and renal replacement therapy at day of or within 30 days after positive test for SARS-CoV-2. Secondary outcomes will be obtained from the Danish National Registry, 3rd version (LPR3).²⁴ While the coding has not yet been validated in this LPR3, admission to ICU, mechanical ventilation, and renal replacement therapy are all registered accurately (positive predictive values 96%-100%) in LPR2 as this is also the platform for mandatory reporting to the national database for quality of intensive care.^{28,29}

Finally, in the risk analysis, we identified patients with positive tests among all patients tested for SARS-CoV-2.

[figure not shown]

Figure illustrating the endpoints in the COVID-19 risk analysis and the endpoints in the COVID-19 prognosis analysis.

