4.4. Study population

The source population is all Danish citizens (popuation~5.8 million).²² The study population for risk analysis (the test-negative case-control analysis) will be all patients tested for SARS-CoV-2, while the prognosis analysis (cohort analysis) will only include patients tested positive SARS-CoV-2, *i.e.*, patients with COVID-19.

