4.5. Follow-up

Patients will be followed from the date of the first RT-PCR test for SARS-CoV-2 that turns out to be positive and up to 30 days after that date for all the outcomes. In a sensitivity analysis follow-up for hospitalization will be restricted to 14 days after first positive test.

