4.8.2. Selection bias

The risk of selection bias is reduced by including all tested Danish inhabitants. Still, criteria for testing and hospital admission have changed during the study period, which will be addressed in a sensitivity analysis stratified by calendar time. We do not expect that ACE-I/ARB users would be more likely to be tested, and thereby included, as compared to users of other antihypertensive drugs.

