4.9. Statistical analyses

In the analyses of prognosis, patients will be followed from day of SARS-CoV-2 positive test result and until date of hospital admission, ICU admission (in analysis of ICU admission), date of death, end of follow-up or for up to 30 days.

Patient characteristics will be tabulated according to each exposure group.

Descriptive analyses will explore the timing of outcomes one month prior to and three months after the first positive test for SARS-CoV-2. In case of a substantial fraction of outcomes having occurred in the days leading up to a positive test, a post-hoc analysis with a larger follow up windows (pre- and post-test) will be conducted.

For each exposure group, we will estimate the 30-day PS-weighted cumulative incidence (risk) of of death, and of each of the non-fatal events (hospital admission, ICU admission, ICU+MV, ICU+inotropes/vasopressors, RRT) accounting for competing risk by death. All 95% confidence intervals will be computed using bootstrapping. The risk of each outcome within 30 days will be computed with 95% CI.

Propensity scores for each comparison (e.g. current ACE-I/ARB use vs. current CCB use) will be computed using logistic regression including all the potential confounders as described above. All other exposures (anti-hypertensive drugs) will be included in the PS-model. The propensity score weighted (SMRW=ATT) cumulative incidence (risk) of each outcome will be plotted and estimated with 95% CI estimated by bootstrapping. The adjusted (PS weighted) risk difference will be computed for the 0-30 period.

The 30-day risk will be compared using PS weighted log binomial regression to estimate risk ratio for death, hospital admission, ICU admission, ICU+MV, RRT, and ICU+inotropes/vasopressors.

Subgroup analysis will be conducted to address effect modifiers including age group (=<65, >65 years) and in patients with assumed uncomplicated hypertension as the primary indication for treatment, defined as patients without any history of diabetes, renal disease, angina pectoris, myocardial infarction, or heart failure. We will also stratify by ABO blood type, if available, because blood type is suggested to be associated with ACE2.³⁰

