The risk of COVID-19 (a positive test for SARS-CoV-2) will be analyzed using a testnegative case-control design among all patients tested. All covariates will be tabulated for patients with a positive test and negative test for SARS-CoV-2. The odds ratio for current ACE-I/ARB use vs. non-use and CCB use, respectively, will be estimated using two separate logistic regression models adjusted for all covariates, see Appendix.

In a sensitivity analysis, we will explore the robustness of our findings by repeating the analyses in patients who filled a prescription within 120 days before a positive test.

Finally, we will do a sensitivity analysis stratified by calendar time to address changes in testing and hospitalization strategy.

10

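### Hospital admissions on the test day count as events in a cohort entered by a positive test, so the admission estimates may shift with test policy, in a direction the protocol does not settle

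*Protocol*

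**What the plan says.** Protocol 4.4 states that "the prognosis analysis (cohort analysis) will only include patients tested positive SARS-CoV-2". Protocol 4.5 sets time zero: "Patients will be followed from the date of the first RT-PCR test for SARS-CoV-2 that turns out to be positive". In 4.7, hospital admission is a secondary outcome, counted "at day of or within 30 days after a positive test in patients not already admitted before the date of the test". An admission on the day of the swab is therefore an event, and a patient admitted earlier is left out of this outcome.

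In 4.9 the plan gives weighted cumulative incidences for each exposure group and two contrasts: "The 30-day risk will be compared using PS weighted log binomial regression to estimate risk ratio for death, hospital admission", among other outcomes, and "The adjusted (PS weighted) risk difference will be computed for the 0-30 period". No odds ratio is planned for the prognosis cohort.

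On selection, 4.8.2 grants that "criteria for testing and hospital admission have changed during the study period". The response in 4.9 is that "we will do a sensitivity analysis stratified by calendar time to address changes in testing and hospitalization strategy". Three other provisions bear on timing:
- a 14-day follow-up analysis for hospitalization (4.5);
- a description of when outcomes occur around the test (4.9);
- a wider window, post hoc, if many outcomes turn out to precede the test (4.9).

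**The concern.** An infected person who is admitted is likely to be swabbed that day. An infected person who stays at home may never be tested. If so, the outcome helps to decide who is in the cohort, and the proportion admitted reflects the swabbing of people at home as well as the course of the disease.

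Two things are at stake. A real difference in admission risk could be misjudged in size and, against some comparators, in direction. In addition, the calendar-time analysis compares periods with different testing, so a change in test policy could be read as a change in the drug's effect. Section 4.8.2 treats selection only as a question of whether ACE-I/ARB users are tested more than users of other antihypertensives. It does not consider selection on the outcome.

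**Working it through.** The protocol gives no figure on this point. Its only power figure (4.10) concerns death.

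**Inputs.** From the protocol: entry by positive test, day 0 included in the event window, risk ratio (RR) and risk difference (RD) as contrasts. Assumed, because the documents give no value: true admission risk in infected comparators r0 = 5%, all admitted cases tested that day, and a share s of non-admitted cases tested.

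**Formula.** With true risk r, the risk observed among test-positives is q = r / (r + (1 − r)s). Then RR = q1/q0 and RD = q1 − q0.

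**Testing independent of exposure.** Example with true RR 1.5 (r1 = 7.5%) and s = 0.1:
- q0 = 0.05 / (0.05 + 0.095) = 0.345
- q1 = 0.075 / (0.075 + 0.0925) = 0.448
- RR = 1.30, RD = 10.3 points

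| s | RR if true 1.2 | RD (true 1.0 point) | RR if true 1.5 | RD (true 2.5 points) |
|---|---|---|---|---|
| 0.5 | 1.19 | 1.8 | 1.47 | 4.4 |
| 0.2 | 1.16 | 3.4 | 1.39 | 8.0 |
| 0.1 | 1.13 | 4.5 | 1.30 | 10.3 |
| 0.05 | 1.09 | 4.8 | 1.21 | 10.6 |

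The odds ratio (OR) stays at 1.21 and 1.54. For r0 between 2% and 10%, the attenuation runs from negligible (1.20 to 1.195 at r0 = 2%, s = 0.5) to large (1.50 to 1.13 at r0 = 10%, s = 0.05). The RD need not rise steadily as testing falls. At r0 = 10% and true RR 1.2 it is 2.0 points at s = 1, 5.1 at s = 0.1 and 4.2 at s = 0.05.

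**Weaker versions of the mechanism** (r0 = 5%, s = 0.1, true RR 1.2). If only half of admissions prompt the test, the observed RR is 1.16. If 30% to 60% of admitted cases drop out because they were swabbed after the admission date, it is 1.15 to 1.17.

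**Testing dependent on exposure** (r0 = 5%, s = 0.1 in the unexposed).
- Exposed non-admitted cases tested 1.25 times as often: q1 = 0.05 / (0.05 + 0.95 × 0.125) = 0.296, so a true RR of 1.0 is observed as 0.296/0.345 = 0.86. A true 1.2 is observed as 0.98.
- Tested 0.8 times as often: 1.0 is observed as 1.15, and 1.2 as 1.29.

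The OR is divided by the testing ratio, so for a true RR of 1.0 it is 0.80 or 1.25, further from 1 than the RR.

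**Planned checks.** Within a calendar stratum s still applies. With a constant true RR of 1.5, a stratum with s = 0.05 shows 1.21 and one with s = 0.2 shows 1.39. The 14-day analysis shortens the far end of follow-up and keeps day 0. The wider window adds time before the test and does not separate swabs prompted by admission. Calendar time in the propensity model (4.8.1.1) balances the exposure groups over time and leaves s unchanged.

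**Death.** Take the 4% comparator mortality of 4.10 as the observed risk and an unchanged OR of 1.2. The exposed odds are 1.2 × 0.04/0.96 = 0.05, the risk is 0.05/1.05 = 4.76%, and the RR is 1.19. With testing equal by exposure, the RR for death is barely attenuated.

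**The case against.** The strongest reply is that the protocol defines its cohort as test-positive patients, and for that population the RR and RD are not wrong. This stands. The bias is relative to all infected persons, so a reader who concludes that the planned RR is invalid goes too far. The distinction still needs stating, because 4.4 equates a positive test with having COVID-19.

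Second, no passage says that admission triggers testing, and none gives an admission risk or a share of infections tested. This also stands: the mechanism is inferred and its size is illustrative. A reader might take 4.9 to expect outcomes to cluster at the test. It only plans to explore their timing, with a conditional follow-up analysis. That description could reveal day-0 clustering, but it does not change the estimates.

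Third, a reader might infer that the RR is always pulled towards 1. That requires testing of non-admitted cases to be independent of exposure. Section 4.8.2 assumes this only against users of other antihypertensives, whereas 4.6 makes non-use one of the two main comparators.

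Fourth, the OR might seem the natural replacement. It is unaffected only under that same independence. It also moves with admission criteria, which 4.8.2 says changed: a constant RR of 1.5 corresponds to an OR of 1.54 at a 5% baseline risk, 1.59 at 10% and 1.71 at 20%.

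Finally, an extra analysis could be left to a statistical analysis plan. However, the protocol itself fixes the event window, the contrasts and the stratified remedy, and those are what is questioned here.

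**Conclusion.** The point holds in a limited form. Counting test-day admissions in a cohort entered by a positive test makes the absolute admission risks, RD and RR depend on who is tested, provided that admission prompts at least some tests. With testing independent of exposure and an assumed comparator risk of 5%, a true RR of 1.5 is observed as 1.47 to 1.21, and the RD moves from 2.5 points to between 4.4 and 10.6, as the share of non-admitted cases tested falls from 50% to 5%. With testing dependent on exposure, the direction is open. The real size cannot be obtained from the protocol.

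The planned checks leave day-0 admissions in, so differences between calendar strata cannot be attributed to the drug alone. Admission is a secondary outcome. A reader might infer that the primary result is compromised in the same way, but death is not defined by a test-day admission and, at about 4% risk, its RR is little attenuated. This is a worthwhile, inexpensive improvement and not a fatal flaw.

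**What to change.** In 4.7 and 4.9:
- Report admissions on day 0 separately from admissions on days 1-30, by exposure group.
- Add a sensitivity analysis of days 1-30 in patients not admitted by day 0, overall and by calendar stratum.
- State that the admission RR and RD apply to test-positive patients under the test policy of the time, and that differences between calendar strata may reflect that policy.
- Optionally, show a propensity-score-weighted OR beside the RR and RD. It should not replace them across strata.

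All of this uses data already planned for and removes nothing. The cost is fewer events and less precision in the day 1-30 analysis. That analysis also covers only patients not admitted by the test day, so it supplements the planned one and does not replace it.

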4.8. Bias

4.8.1. Confounding

Confounding will be handled by using propensity score (PS) methods. In addition, the use of an active comparator design reduce confounding by indication, as most users of the comparator are also likely to have hypertension as the indication for treatment. To further reduce confounding by indication, we will repeat the analyses after restriction to patients without history of heart or kidney disease, which are other indications for ACE-I/ARB use. Although we included a large number of coexisting conditions, life-style factors and co-medication, we cannot exclude the impact of unmeasured confounding, e.g., by severity of condition indication ACE-I/ARB treatment. As we lacked detailed data on severity of heart and renal diseases, we reduced confounding in a subgroup analysis of patients without any history of these diseases.

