4.8.1.1. Propensity score methods

The PS is the probability of being exposed given the covariate pattern for the patient. The PS will be estimated for each patient hospitalization in each of the examined comparisons using a logistic regression model including calendar time and the covariates listed in the Appendix. As we are interested in the average treatment effect in the treated (ATT), we apply PS-weighting using ATT weights to make the number and covariate distribution in the comparison groups resemble that of the ACE-I/ARB users.

8

Overlap in PS distributions will be checked before weighting. Covariate balance will be assessed by standardized differences (SDs), empirical cumulative distribution functions for continuous variables (age and index), and by PS-weight percentiles.

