4.10. Sample size considerations

As of 20 April 2020, there are 96,224 individuals tested for SARS-CoV-2 and 7,515 are tested positive. A total of 364 patients with a positive test have died (4.8%). The proportion of patients using ACE-I/ARB is expected to be 17% and the proportion using CCB is expected to be 7% based on data from a historical cohort of patients with influenza or pneumonia ([name] et al., article submitted).

Assuming a 30-day mortality of 4% in unexposed, we will have a power of 92% for detecting a RR of 1.2 with an alpha-level of 5% in the comparison of current ACE-I/ARB users with non-users. (EpiSheet).

5. Ethical/data protection issues

According to Danish law, registry-based studies do not require informed consent or ethical committee approval. Only aggregated data will be published.

All data are pseudonymized and stored at secured serves at the Danish Health Data Authority. Data management and analyses are performed through secure remote access to these servers. Data management and analyses will be conducted and checked by experienced researchers.

6. Plans for communication of study results

[figure not shown]
The study protocol will be registered in the EU PAS registry. Results will be communicated through international peer-reviewed journals and the website of the Danish Medicines Agency. Any evidence of adverse effects of ACE-I/ARB will be communicated to the Danish Medicines Agency.

7. Amendments and deviations

Any future amendments or deviations from the study protocol will be included in this section.

Figure. Study design diagram

Study design

Codes

	Source/	Look-	Inclusion codes	Exclusion
	coding	back		codes
Exposures (ATC codes)				
Number of antihypertensives	NPD/ATC	90d	0-5 (see below: ACE-I/ARB, CCB, Thiazides/diuretics, BB, other antihypertensives)	
ACE-I	NPD/ATC	90d	C09A, C09B	
ARB	NPD/ATC	90d	C09C, C09D	
Calcium channel blockers (CCB)	NPD/ATC	90d	C07FB, C08CA, C09BB, C09DB, C09DX01	
Thiazides/diuretics	NPD/ATC	90d	C03AA01, C03AA03, C03AB01, C03AB03, C03AX01, C03EA, C07B, C09BA, C09DA, C09DX01, C09DX03, C09XA52, C09XA54	C07BA06 C09BA04
Beta-blockers (BB)	NPD/ATC	90d	C07	
Other antihypertensives	NPD/ATC	90d	C02AC, C02CA, C03BA11, C09XA C02AB01	C09XA54
Outcomes				
ICU admission (procedure code)	DNPR/Procedure		NABE, NABB	
Mechanical ventilation (procedure code)	DNPR/Procedure		BGDA0	

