Aspirin	NPD/ATC	90d	B01AC06, N02BA01, N02BA51
Opioid use	NPD/ATC	90d	N02A, N07BC02
Immunosuppressant use	NPD/ATC	90d	L04
Glucocorticoids	NPD/ATC	90d	H02AB
Loop diuretics	NPD/ATC	90d	C03C
Antibiotics	NPD/ATC	10d	J01
Antivirals	NPD/ATC	10d	J05
Vitamin K antagonists	NPD/ATC	90d	B01AA
Antidepressants	NPD/ATC	90d	N06A
Antipsychotics	NPD/ATC	90d	N05A
Hypnotics/sedatives	NPD/ATC	90d	N05C
Marital status	CPR		
Rural/urban place of residence	CPR		

Abbreviations: ATC Anatomical Therapeutic Chemical Classification System; CPR Danish Civil Reigistration System; DNPR Danish National Patient Registry; ICD-10 International Classification of Diseases 10th edition; NPD National Prescription Database.

References:

- 10. Sommerstein R, Gräni C. Rapid response: re: preventing a covid-19 pandemic:

ACE inhibitors as a potential risk factor for fatal Covid-19. https://www.bmj.com/content/368/bmj.m810/rr-2. *BMJ.* 2020.

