For each question of the Checklist, the investigator should indicate whether or not it has been addressed in the study protocol. If the answer is "Yes", the section number of the protocol where this issue has been discussed should be specified. It is possible that some questions do not apply to a particular study (for example, in the case of an innovative study design). In this case, the answer 'N/A' (Not Applicable) can be checked and the "Comments" field included for each section should be used to explain why. The "Comments" field can also be used to elaborate on a "No" answer.

This Checklist should be included as an Annex by marketing authorisation holders when submitting the protocol of a non-interventional post-authorisation safety study (PASS) to a regulatory authority (see the Guidance on the format and content of the protocol of non-interventional post-authorisation safety studies). The Checklist is a supporting document and does not replace the format of the protocol for PASS presented in the Guidance and Module VIII of the Good pharmacovigilance practices (GVP).

Study title: Renin-angiotensin-aldosterone system inhibitors and adverse outcomes of COVID-19: a Danish nationwide cohort study

EU PAS Register[®] number: Study reference number (if applicable):

Sec t	ion 1: Milestones	Yes	No	N/A	Section Number
1.1	Does the protocol specify timelines for				
	1.1.1 Start of data collection ¹	\square			1
	1.1.2 End of data collection ²	\square			1
	1.1.3 Progress report(s)			\square	

¹ Date from which information on the first study is first recorded in the study dataset or, in the case of secondary use of data, the date from which data extraction starts.

² Date from which the analytical dataset is completely available.

Section 1: Milestones	Yes	No	N/A	Section Number
1.1.4 Interim report(s)			\boxtimes	
1.1.5 Registration in the EU PAS Register $^{ m extsf{ iny R}}$	\bowtie			1
1.1.6 Final report of study results.	\square			1

Sect	Section 2: Research question			N/A	Section Number
2.1	Does the formulation of the research question and objectives clearly explain:				
	2.1.1 Why the study is conducted? (e.g. to address an important public health concern, a risk identified in the risk management plan, an emerging safety issue)	\boxtimes			2
	2.1.2 The objective(s) of the study?	\square			3
	2.1.3 The target population? (i.e. population or subgroup to whom the study results are intended to be generalised)	\boxtimes			2

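### The Appendix covariate list has no code for aldosterone antagonists, an available dispensing marker of heart-disease severity; the remaining bias is probably small and the remedy is one code row

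*Protocol*

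**What the plan says.** Section 4.8.1.1 fixes the adjustment set: the propensity score is estimated "using a logistic regression model including calendar time and the covariates listed in the Appendix". Section 4.9 adds that "All other exposures (anti-hypertensive drugs) will be included in the PS-model", and adjusts the two test-negative logistic models for all Appendix covariates as well.

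The Appendix code table lists drugs at ATC level. The count of antihypertensives is "0-5 (see below: ACE-I/ARB, CCB, Thiazides/diuretics, BB, other antihypertensives". The thiazide/diuretic row reads "C03AA01, C03AA03, C03AB01, C03AB03, C03AX01, C03EA, C07B, C09BA, C09DA, C09DX01, C09DX03, C09XA52, C09XA54". Among the co-medications, "Loop diuretics" (C03C) have a 90-day look-back. The renin-inhibitor group C09XA is included under other antihypertensives.

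On severity, section 4.8.1 gives the severity of the condition indicating treatment as an example of possible unmeasured confounding. It continues "As we lacked detailed data on severity of heart and renal diseases" and turns to patients without a history of these diseases. Section 4.6 describes the prescription register as complete for community-pharmacy fills since 1995, with dispensing date, ATC code and quantity.

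**The concern.** Among patients with a heart-failure diagnosis, those who also fill an aldosterone antagonist tend to have more advanced disease and are often on an ACE-I or ARB too. This is general pharmacology and is not stated in the Protocol. If it holds in these data, two patients with the same diagnosis and the same loop-diuretic status may still differ in severity, and the more severe one is more likely to be in the exposed group. ATT weighting balances only what is in the propensity model, so part of this difference could remain in the main mortality comparison. It would then push the risk ratio towards apparent harm from ACE-I/ARB.

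The Protocol speaks of lacking severity data while the linked register holds a usable partial marker. It already uses another dispensing marker of the same kind, loop diuretics.

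**Working it through.** **1. Is the omission real?** The ATC codes for aldosterone antagonists (C03DA01, C03DA02, C03DA04) were matched by prefix against every ATC code in the Appendix table.

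- C03DA01, C03DA02, C03DA04: no match. C03EB01, the high-ceiling plus potassium-sparing combination: no match.
- Controls for the method: C03CA01 matches C03C (loop diuretics), and C09XA02 matches C09XA (other antihypertensives).

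The drugs therefore enter neither the propensity model nor the test-negative models, and the 0-5 count does not register them. C03DA is the right level: C03D also holds potassium-sparing drugs that are not aldosterone antagonists.

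**2. What already adjusts for severity?** Covariates include hospital-diagnosed heart failure, myocardial infarction, valve disease, atrial fibrillation, kidney disease, end-stage renal disease and loop diuretics. Beta-blockers enter as another antihypertensive group. Section 4.8.1 repeats the analyses without heart or kidney disease. Section 4.9 adds a subgroup with assumed uncomplicated hypertension. The gap therefore concerns mainly the unrestricted main estimates.

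**3. How large could the bias be?** The Protocol states no figure to reproduce. The standard factor for an omitted binary confounder is

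B = [1 + p1(RR - 1)] / [1 + p0(RR - 1)],

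where p1 and p0 are the shares using the drug among ACE-I/ARB users and comparators after weighting, and RR is the mortality ratio linked to use beyond the listed covariates. All three inputs are assumptions.

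| p1 vs p0 | RR 1.3 | RR 1.5 | RR 2.0 |
|---|---|---|---|
| 4% vs 2% | 1.012/1.006 = 1.006 | 1.02/1.01 = 1.010 | 1.04/1.02 = 1.020 |
| 6% vs 2% | 1.018/1.006 = 1.012 | 1.03/1.01 = 1.020 | 1.06/1.02 = 1.039 |
| 8% vs 2% | 1.024/1.006 = 1.018 | 1.04/1.01 = 1.030 | 1.08/1.02 = 1.059 |
| 5% vs 1% | 1.015/1.003 = 1.012 | 1.025/1.005 = 1.020 | 1.05/1.01 = 1.040 |

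The range is 1.006 to 1.059. Equal use (5% vs 5%) gives 1.00 at any RR. The corner 8% vs 1% with RR 2.0 gives 1.08/1.01 = 1.07. A more extreme set, 10% vs 3% with RR 3, gives 1.20/1.06 = 1.13.

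**4. Scale.** Section 4.10 plans around a risk ratio of 1.2, so the top of the grid is 0.059/0.2, about 30% of that excess; the central case (6% vs 2%, RR 1.5) is 0.020/0.2, about 10%. For random error, take section 4.10's 7,515 positives, 17% exposed (1,278 against 6,237) and risks of 4.8% and 4%. The crude standard error of log RR is √[0.952/(0.048 × 1,278) + 0.96/(0.04 × 6,237)] = 0.139. The 95% interval runs from the estimate divided by exp(1.96 × 0.139) = 1.31 to the estimate multiplied by it. The possible bias is small beside that.

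**The case against.** The strongest reply is that this is one more covariate for an already long list. Severity is substantially adjusted for. The quoted sentence speaks of detailed severity data, and a dispensing record is not that, so the sentence is not false. The size rests wholly on assumed inputs, and nothing in the Protocol shows that use would be higher among the exposed after weighting. Most of this stands, and it limits the weight of the point. It does not remove the point: restriction is a secondary analysis and leaves the main estimate unchanged. It also relies on hospital diagnoses, so heart disease never coded in hospital stays in the restricted group.

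Two stronger readings are tempting. The checklist title, "Renin-angiotensin-aldosterone system inhibitors and adverse outcomes of COVID-19: a Danish nationwide cohort study", might lead a reader to infer that comparators taking an aldosterone antagonist are wrongly counted as free of RAAS blockade. The documents do not support this: sections 3 and 4.6 define exposure and non-use by ACE-I/ARB alone, and nowhere promise a reference group free of all RAAS drugs. A reader might also infer that severity is handled by restriction only; the covariate list shows otherwise.

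**Conclusion.** The point holds as a modest, specific improvement to the adjustment set. The omission can be verified in the code table, and the covariate lists for both sets of models are fixed by the Protocol. The likely effect on the mortality ratio is a factor of about 1.01-1.06 under the assumed prevalences and mortality ratios, 1.00 if use is balanced, and more only under extreme inputs. The direction towards harm is plausible against non-users and CCB users, less certain against beta-blocker users, and not established by the documents. The calculation covers mortality only; no size is offered for the test-negative odds ratio.

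A reader might extend the point to anticoagulation, which is coded only as "Vitamin K antagonists". No bias argument supports that extension, and atrial fibrillation and venous thromboembolism are already covariates, so it forms no part of this conclusion.

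**What to change.** Add a row for aldosterone antagonists (C03DA, 90-day look-back, as for loop diuretics) to the Appendix covariates, and include it in every propensity-score model and in both test-negative logistic models. Report its standardized difference before and after weighting, which will show directly whether the imbalance assumed above exists. Qualify the sentence in section 4.8.1 to say that clinical severity measures are not available but that dispensing proxies for severity are used.

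A sensitivity analysis leaving users of these drugs out of the comparator groups is optional.

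The cost is one extra code row and one more term per model. The register is already linked, so no new data are needed, and the sample size does not change.
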